## 13. STATISTICAL CONSIDERATIONS

### 13.1 Study Design/Endpoints

This phase II study will randomize patients 2:1 to Arm A (T/C/V) or to the standard Arm B (T/C), respectively. The primary end point is Overall Response (CR/CRi). We expect that these MPN patients will fall into two risk categories based on the percent blasts at baseline: < 20% blasts versus 20% or higher. The expected CR/CRi rate with traditional regimens in this group of patients ranges from 14% for patients with worse disease to 29% for patients with blasts 20% or higher.

For each group, the level of response that would confer interest in pursuing the therapy is a CR/CRi rate of 58%. This CR/CRi response rate was the response rate seen in our phase I trial in the subset of MPN patients with a lower response rate (those with less than 20% blasts), where we observed responses in 7 out of 12 cases (58.3%). The proportion of patients in each subgroup are assumed to be 33% in the low blast count group and 67% in the higher blast count group, respectively. These proportions are considered in the sample size calculation. The final analysis will be by an exact Cochrane-Mantel-Haenszel test, which tests for an overall treatment difference while adjusting for subgroup. The primary analysis will conclude a significant benefit for Arm A over Arm B if the one-sided p value < 0.10.

The study design includes interim monitoring for futility (i.e., stopping early if there is high probability that the study will not show a significant benefit for Arm A over Arm B). Futility is based on the predictive probability of a statistically significant treatment difference at the end of the study if the study enters, treats, and follows the total number of patients planned for the study. If we determine at any interim analysis that there is a < 10% chance of ultimately finding a statistically significant difference between Arm A and Arm B, we will pause for a safety review by the PI, study team, and CTEP if one of the stopping boundaries is hit. We determined the predictive probability of a significant trial result through simulations using a beta-binomial model to predict future observations conditional on data available at the time of the test. In the simulations, the predicted test was an exact Cochran-Mantel-Haenszel test, and a predicted test was significant if the one-sided p value of the test was < 0.10, as stated in the primary analysis.

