### 13.2 Sample Size/Accrual Rate

We expect to enroll 1-2 patients per month at JHU alone. With 7-8 other centers participating in this study, we expect their accrual to average 3 patients per month, for a study-wide total of 3 patients per month. We fully expect that we will be able to complete accrual in 12-16 months, allowing for some patients who may drop out before randomization, and accrual holds for interim analysis.

The futility analysis will begin when 24 patients (16 in Arm A, 8 in Arm B) have entered the study and received treatment. If the study does not stop after the first interim analysis, a second interim analysis will be done when another 18 (12 in Arm A, 6 in Arm B) patients have entered the study and received treatment (42 patients total). Each interim analysis will project the remaining patients yet to be enrolled and compute the predicted significance level of the primary analysis, conditional on the data available at the time of analysis (i.e., predictive power).

The prior distribution for the interim futility analyses is a non-informative beta(1,1) prior. Provided the study does not stop for futility, the final sample size will be 60 patients, with 40 in Arm A and 20 in Arm B.

The operating characteristics of the design are shown in the table below. We performed 1,000 simulations with varying values of the underlying probability of a response for each treatment and disease subgroup. The table shows that this study will have approximately 91% power to detect an increase (given in the first paragraph of this section) in the subgroup-specific probabilities of a complete response for Arm A compared to Arm B.

Sample Size (A / B)	Probability of a CR in < 20% blasts group (A / B)	Probability of a CR in 20% or higher blasts group (A / B)	Estimated Power	Probability of stopping early at each interim analysis (1st / 2nd)	Cumulative probability of stopping early	Probability of failing to reject at the end of the study
40 / 20	0.58 / 0.29	0.58 / 0.14	0.91	0.042 / 0.014	0.056	0.034
	0.40 / 0.29	0.40 / 0.14	0.475	0.182 / 0.125	0.307	0.218
	0.29 / 0.29	0.14 / 0.14	0.036	0.638 / 0.214	0.852	0.112

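### Section 13.1 contradicts itself on what follows a futility crossing, and the 13.2 stopping probabilities hold only if a crossing ends enrolment

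*Combined protocol and SAP*

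**What the plan says.** Section 13.1 explains futility monitoring as "stopping early if there is high probability that the study will not show a significant benefit for Arm A over Arm B". The criterion is a predictive probability, assessed at each interim analysis: the rule is triggered if "there is a < 10% chance of ultimately finding a statistically significant difference between Arm A and Arm B". The same sentence then gives the action: "we will pause for a safety review by the PI, study team, and CTEP if one of the stopping boundaries is hit".

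Section 13.2 is written as though a crossing ends the trial. The second look takes place "If the study does not stop after the first interim analysis", and "Provided the study does not stop for futility, the final sample size will be 60 patients". The operating-characteristics table has columns for stopping at each look and for "Cumulative probability of stopping early". Its null row gives 0.638 at the first look and 0.214 at the second, 0.852 in total.

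Section 13.4 sets up toxicity monitoring as something additional to futility monitoring. It has its own boundaries, its own hold on enrolment and its own safety consultation with CTEP.

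**The concern.** The trigger and the action belong to different questions. The trigger is a low chance of showing that veliparib adds benefit. The action is a review of safety. A safety review can find nothing wrong in a trial that has almost no chance of a positive result, and the text does not say what should then happen. It gives no criterion for ending or resuming the trial and does not say who makes that decision.

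Futility stopping limits how many patients are enrolled when the three-drug arm is no better than the control arm. The table credits the design with that protection at 85% under the null. A reader relying on the table would take 0.852 as a property of the design, although the action sentence does not commit the trial to stopping.

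The wording also matters because the review is assigned to the PI, the study team and CTEP, while Section 12.1 gives the PI and statistician access to the data at all times. The plan assigns this decision to no independent committee, so the written rule is the main safeguard.

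**Working it through.** **1. Does the table treat every crossing as a stop?** The inputs are three columns of the 13.2 table: power, cumulative probability of stopping early, and probability of failing to reject at the end.

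| Response rates A / B (<20% blasts; ≥20% blasts) | Power | Stopped early | Fail at end | Sum |
|---|---|---|---|---|
| 0.58 / 0.29; 0.58 / 0.14 | 0.91 | 0.056 | 0.034 | 1.000 |
| 0.40 / 0.29; 0.40 / 0.14 | 0.475 | 0.307 | 0.218 | 1.000 |
| 0.29 / 0.29; 0.14 / 0.14 | 0.036 | 0.852 | 0.112 | 1.000 |

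A trial that crossed, resumed and reached its final analysis would fall in two of these categories, and the row would exceed 1. The sums show that the simulation ended the trial at every crossing.

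**2. Can the table be reproduced under that rule?** Exact enumeration was used with the plan's one-sided exact Cochran-Mantel-Haenszel test at p < 0.10, beta(1,1) priors by arm and stratum, looks at 16/8 and 28/14, and a final 40/20. The plan does not give stratum sizes by arm and look. Assumed sizes (A/B) at the two looks and the end were 5/3, 9/5 and 13/7 for low blasts, and 11/5, 19/9 and 27/13 for high blasts.

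| | Enumerated | Table |
|---|---|---|
| Design alternative: power | 0.908 | 0.91 |
| Design alternative: stopped early | 0.054 | 0.056 |
| Null: rejection | 0.043 | 0.036 |
| Null: stopped early | 0.825 | 0.852 |

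Power is reproduced. The null stopping figure is 0.027 lower, about 2.4 Monte Carlo standard errors of the table's own estimate: √(0.852 × 0.148 / 1,000) = 0.011. Because the stratum sizes and the number of predictive draws are not stated, this gap is not evidence of an error in the table.

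**3. Expected enrolment under the null if every crossing stops the trial** (table figures). The probability of reaching 60 is 1 − 0.852 = 0.148.

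24 × 0.638 + 42 × 0.214 + 60 × 0.148 = 15.31 + 8.99 + 8.88 = 33.2 patients.

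**4. If crossings are overridden.** If all are, 60 patients enrol: 60 − 33.2 = 26.8 more, which is the upper limit. If a share q of crossings resumes, the stopping probability is roughly 0.852 × (1 − q). This ignores a second crossing at 42 patients, which would raise the figures somewhat.

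| Share resumed | Probability of stopping early |
|---|---|
| 0% | 0.852 |
| 25% | 0.64 |
| 50% | 0.43 |
| 75% | 0.21 |
| 100% | 0 |

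**5. Error rates without any stopping** (enumeration, same assumed strata). Null rejection is 0.049, against 0.043 with stopping. Power is 0.932, against 0.908 with stopping. Another rounding of the strata gives 0.0515 and 0.940, and random strata give 0.0493 and 0.930. All the null figures are well below 0.10.

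**The case against.** The strongest reply is that the plan, read as a whole, says the trial stops. Section 13.1 introduces the procedure as early stopping, and the action sentence itself calls the limits stopping boundaries. Section 13.2 twice assumes that the study may have stopped. Section 13.4 treats toxicity in much the same way: it says the trial will stop, then describes a hold on enrolment and a consultation with CTEP. A pause followed by CTEP review may simply be this protocol's usual route to a stop. On that reading the table describes the intended rule, and the action sentence is loosely worded.

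Most of this stands. A reader might infer that crossing triggers nothing more than a pause, or that a safe but futile trial would be cleared to resume. The documents do not support either inference: the surrounding text speaks of stopping, and no passage says that a trial found safe continues. It would also be too strong to say that the table describes a different rule, since it agrees with the rest of 13.1 and 13.2. And the null row means no added benefit over topotecan and carboplatin, not a regimen without activity.

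What the reply does not supply is a decision. The phrases about stopping presuppose a stop. The only sentence that attaches an action to the threshold names a review on another subject and gives it no outcome. That contradiction remains however likely the intent.

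**Conclusion.** The concern holds as an internal contradiction in a stated rule, with stopping as the probable intent. The figure 0.852 is the simulated chance of crossing a boundary. It is also the chance of stopping early, with expected null enrolment of about 33, provided that crossing ends enrolment.

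The consequence is limited to the early-stopping probability and the expected sample size. The figure of about 27 further patients is an upper bound that requires every crossing to be overridden in a trial with no treatment difference; it is not a forecast. A reader might also infer that continuing past a crossing inflates the type I error. It does not: null rejection stays at about 0.05 against the 0.10 level, and power rises slightly to about 0.93. These last figures rest on assumed stratum sizes near 1/3 and 2/3. The enrolment figures come from the table alone.

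**What to change.** Replace the action sentence in Section 13.1 so that it agrees with the rest of 13.1 and with 13.2. For example: *If the predictive probability is below 10% at either interim analysis, enrolment stops for futility; any decision to continue is documented with CTEP, with its reasons.* Describe the safety review in a separate sentence as a separate step, and leave the toxicity rule in 13.4 as it is. The table then needs no change.

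Only if the sponsor declares the rule non-binding is more needed: relabel 0.852 and the matching entries in the other rows as probabilities of crossing the boundary, and add the operating characteristics without stopping.

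The cost is one or two sentences, plus a relabelling and additional columns in the non-binding case. The sample size, test and significance level do not change. The wording should be settled before an interim look, because a rule interpreted after a crossing is no longer prespecified.

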### 13.2 Sample Size/Accrual Rate

We expect to enroll 1-2 patients per month at JHU alone. With 7-8 other centers participating in this study, we expect their accrual to average 3 patients per month, for a study-wide total of 3 patients per month. We fully expect that we will be able to complete accrual in 12-16 months, allowing for some patients who may drop out before randomization, and accrual holds for interim analysis.

The futility analysis will begin when 24 patients (16 in Arm A, 8 in Arm B) have entered the study and received treatment. If the study does not stop after the first interim analysis, a second interim analysis will be done when another 18 (12 in Arm A, 6 in Arm B) patients have entered the study and received treatment (42 patients total). Each interim analysis will project the remaining patients yet to be enrolled and compute the predicted significance level of the primary analysis, conditional on the data available at the time of analysis (i.e., predictive power).

The prior distribution for the interim futility analyses is a non-informative beta(1,1) prior. Provided the study does not stop for futility, the final sample size will be 60 patients, with 40 in Arm A and 20 in Arm B.

The operating characteristics of the design are shown in the table below. We performed 1,000 simulations with varying values of the underlying probability of a response for each treatment and disease subgroup. The table shows that this study will have approximately 91% power to detect an increase (given in the first paragraph of this section) in the subgroup-specific probabilities of a complete response for Arm A compared to Arm B.

Sample Size (A / B)	Probability of a CR in < 20% blasts group (A / B)	Probability of a CR in 20% or higher blasts group (A / B)	Estimated Power	Probability of stopping early at each interim analysis (1st / 2nd)	Cumulative probability of stopping early	Probability of failing to reject at the end of the study
40 / 20	0.58 / 0.29	0.58 / 0.14	0.91	0.042 / 0.014	0.056	0.034
	0.40 / 0.29	0.40 / 0.14	0.475	0.182 / 0.125	0.307	0.218
	0.29 / 0.29	0.14 / 0.14	0.036	0.638 / 0.214	0.852	0.112

### 13.3 Stratification Factors

At the time of randomization, we will stratify according to 1) marrow blast percentage (<20% vs.  $\geq 20\%$ ).

### 13.4 Early Stopping Guidelines

In addition to monitoring for futility, we will stop the trial if there is evidence of excess toxicity. We plan to monitor each treatment arm separately for the occurrence of any of following adverse events:

- 1) Grade 4 or higher generalized infection or
- 2) Grade 4 or higher radiologically diagnosed lower GI mucositis or
- 3) Grade 3 or higher hand and foot syndrome or
- 4) Grade 3 or higher cardiac arrhythmias or
- 5) Treatment-related mortality or
- 6) Duration of neutropenia exceeding 60 days

Toxicity will be monitored after every 5 patients. If the risk of any of the above adverse events convincingly exceeds 30% in Arm A or 20% in Arm B, the study PI will contact CTEP for a safety consultation. The stopping rule for toxicity will hold enrollment if the posterior probability of risk being larger than 30% (Arm A) or 20% (Arm B) exceeds 0.75. The prior for this toxicity monitoring rule for Arm A is a beta (2,4) distribution and for Arm B is a beta (1,4). This means that our prior guesses at the proportion of severe toxicities is 33% for Arm A and 20% for Arm B. There is a 90% probability that these proportions are between 7.6% and 65.7%, and 1.2% and 52.7%, respectively. The operating characteristics of the stopping rule are shown below and

based on 5000 simulations.

Toxicity Stopping Rules

Arm B			Arm A		
N toxicities	N patients	Probability of too much toxicity *	N toxicities	N patients	Probability of too much toxicity *
3	5	0.914	3	5	0.850
4	10	0.870	5	10	0.869
5	15	0.837	6	15	0.772
6	20	0.811	8	20	0.811
			10	25	0.841
			11	30	0.773
			13	35	0.807
			15	40	0.836

\* The probability of too much toxicity is the posterior probability of toxicity being larger than 20% for Arm A and 30% for Arm B

Operating Characteristics of stopping rule, based on 5000 simulations:

Arm B			Arm A		
True Toxicity Rate	Probability of declaring treatment too toxic	Average sample size	True Toxicity Rate	Probability of declaring treatment too toxic	Average sample size
10%	0.030	19.7	20%	0.113	36.8
15%	0.101	19.2	25%	0.253	33.2
20%	0.263	18.1	30%	0.468	28.1
25%	0.457	16.4	35%	0.660	23.1
30%	0.643	14.7	40%	0.842	17.6
35%	0.805	12.7	45%	0.943	13.5

To ensure balanced randomization between the 2 arms with respect to disease classification, we will stratify up-front according to the two disease categories described above.

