## 5. TREATMENT PLAN

### 5.1 Agent Administration

Treatment will be administered on an inpatient basis. Reported adverse events and potential risks are described in Section 7. Appropriate dose modifications are described in Section 6. No investigational or commercial agents or therapies other than those described below may be administered with the intent to treat the patient's malignancy. Patient's adherence to oral therapy will be documented through hospital charting.

Arm A : Veliparib 80 mg by mouth twice daily days 1-21. Topotecan 1.2 mg/m^2/d and Carboplatin 150 mg/m^2/day continuous intravenous infusion (CIV) over 5 days for a total of 120 continuous hours on days 3-7.

Arm B : Topotecan 1.6 mg/m^2/d and Carboplatin 150 mg/m^2/day continuous intravenous infusion (CIV) over 5 days for a total of 120 continuous hours on days 1-5.

Regimen Description					
Agent	Premedications; Precautions	Dose	Route	Schedule	Cycle Length
Topotecan	Premedicate with minimum of ondansetron 8 mg IV twice daily	ARM A: 1.2 mg/m  /day in 250 mL D5W ARM B: 1.6 mg/m  /day in 250 mL D5W	IV as continuous infusion over 24 hours for 5 days	Days 3-7*** (ARM A) or Days 1-5*** (ARM B)	28 days: if responding, second cycle can be administered as early as day 28 but no later than day 63. Responding patients may receive up to 3 more cycles (4 total) (see Section 6.1 )
Carboplatin		150 mg/m  /day in 250 cc D5W	IV as continuous infusion over 24 hours for 5 days	Days 3-7*** (ARM A) or Days 1-5*** (ARM B)	
Veliparib**		80 mg	PO twice daily	Days 1-21 (ARM A)	

\*\*Randomized administration.  
\*\*\*Begins at the start of Day 3 or 1 and runs for 5 days continuously, i.e., through the end of Day 7 or 5

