## 6. DOSING DELAYS/DOSE MODIFICATIONS

### 6.1 Dosing Delays

Once a cycle is started, prescribed therapy will not be delayed. Patients unable to take veliparib due to toxicity will have those doses skipped.

For patients achieving CR, CRI, PR, or MR following cycle 1, a repeat cycle of the same regimen may be administered beginning no sooner than Day 28 of the preceding cycle and no later than Day 63 from the initiation of the previous cycle (see **Section 5.1**). Delays beyond day 63 should be reviewed with the principal investigator and may be approved if patient is deemed be achieving clinical benefit.

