### 13.5 Analysis of Endpoints

For descriptive purposes, the CR/CRI rate will be reported at the end of the study separately for Arm A and Arm B as intent to treat analysis with exact binomial 95% confidence intervals. The final analysis will be by an exact Cochrane-Mantel-Haenszel test, which tests for an overall treatment difference while adjusting for subgroup. The primary analysis will conclude a significant benefit for Arm A over Arm B if the one-sided p value < 0.10. The odds ratio for the probability of CR/CRI for Arm A versus Arm B will also be estimated using a logistic regression model that adjusts for baseline blast count group, to account for the randomization stratification factor. The estimate will be provided with a 95% confidence interval. The secondary analysis of results will include reporting preliminary estimates of the odds ratio (comparing Arm A over Arm B) for the two blast (risk) groups separately. The differences in the odds ratios (i.e., differential treatment effect) will be described using an interaction analysis from a logistic regression model.

An overall toxicity rate and a rate for each specific toxicity listed above in the early stopping guidelines will be reported for Arm A and Arm B separately and together with exact binomial 95% confidence intervals.

The distribution of mutations in DNA repair defects via assessment in Leukemia mutation panel will be summarized using descriptive statistics. The frequency of patients with functional impairment of DNA damage response via assessment with RAD51 assay will be reported with exact binomial 95% confidence intervals. The association between these biomarkers and response will be described with appropriate tests for continuously measured biomarkers (t tests, Wilcoxon rank sum tests) and categorical biomarkers (Fisher's exact test). These descriptive analyses for addressing secondary objectives will be performed for the whole cohort and also separately for Arms A and B. Differential treatment outcomes for patient subgroups defined by these biomarkers may be explored using appropriate tests for interactions.

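### Toxicity events have no counting window while cycles 2 to 4 depend on response, so by-arm toxicity rates can differ simply because one arm responds more and is treated longer

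*Combined protocol and SAP*

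**What the plan says.** Section 13.4 lists six events and states "We plan to monitor each treatment arm separately for the occurrence of any of following adverse events". "Toxicity will be monitored after every 5 patients", and the rule is to "hold enrollment if the posterior probability of risk being larger than 30% (Arm A) or 20% (Arm B) exceeds 0.75". The priors are beta(2,4) for Arm A and beta(1,4) for Arm B. A crossing leads to a safety consultation with CTEP.

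Section 13.5 adds: "An overall toxicity rate and a rate for each specific toxicity listed above in the early stopping guidelines will be reported", by arm and combined, with exact 95% intervals. Section 1.2 makes comparison of toxicities the first secondary objective.

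None of these sections says which cycles count. Section 13.7.1 gives a start for toxicity evaluation (the first veliparib dose, which Arm B never receives) and no end.

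Section 5.1 allows four cycles in total. Section 6.1 sets who goes on: "For patients achieving CR, CRI, PR, or MR following cycle 1, a repeat cycle of the same regimen may be administered", 28 to 63 days after the previous cycle began. Section 5.3 takes other patients off treatment. Section 5.4 counts minimum follow-up from removal from treatment, so patients who keep responding are also observed for longer.

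**The concern.** A per-patient rate of any listed event grows with the number of cycles given. Here that number depends on response, which is what the arms are expected to differ on. Two arms with identical risk per cycle could therefore show different toxicity rates. A reader of the Section 13.5 table could not tell whether veliparib adds toxicity per cycle or whether Arm A simply received more cycles.

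The same silence affects Section 13.4. Whether a listed event in cycle 3 counts towards a hold is not settled, so two people applying the rule to the same data could reach different answers.

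**Working it through.** **Step 1: reproduce the Section 13.4 tables.** A boundary is the smallest count x among n patients for which the posterior probability of exceeding the limit is above 0.75. For Arm A at n = 5, x = 3, the posterior is beta(2+3, 4+2) = beta(5,6), and P(risk > 0.30) = 0.850, as printed. For Arm B it is beta(1+3, 4+2) = beta(4,6), and P(risk > 0.20) = 0.914, as printed. All 12 boundaries reproduce, using 30% for Arm A and 20% for Arm B as in the text (the table footnote swaps them). An exact recursion over groups of five, with one yes/no outcome per patient, reproduces all 12 probabilities of declaring the arm too toxic. The largest gap is 0.016 (Arm A at 35%: 0.676 against 0.660).

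**Step 2: rate per patient when all cycles count.** Let q be the risk per cycle, r the share starting cycle 2 and K the number of cycles those patients receive. With independent cycles and each patient counted once:

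rate = q + (1 − q) × r × [1 − (1 − q)^(K−1)]

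Inputs:
- r in Arm A: 0.58, the design CR/CRi rate (Section 13.1).
- r in Arm B: 0.33 × 0.29 + 0.67 × 0.14 = 0.19, from the blast-group mix in Section 13.1 and the rates in the Section 13.2 table.
- q: 20% in both arms. This is an assumption; the documents give no risk per cycle.

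Using CR/CRi rates for r is also an assumption. PR and MR patients may continue too, and their rates by arm are not given.

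For Arm A with K = 4: 0.20 + 0.80 × 0.58 × (1 − 0.80³) = 0.20 + 0.464 × 0.488 = 0.426.

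| Cycles counted | Rate, A | Rate, B | Hold probability, A | Hold probability, B |
|---|---|---|---|---|
| Cycle 1 only | 20% | 20% | 0.12 | 0.26 |
| 2 | 29.3% | 23.0% | 0.43 | 0.38 |
| 3 | 36.7% | 25.5% | 0.74 | 0.47 |
| 4 | 42.6% | 27.4% | 0.91 | 0.55 |

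Hold probabilities come from the Step 1 recursion, with every cycle complete by the look. The between-arm gap is 29.3 − 23.0 = 6.3 points with two cycles and 42.6 − 27.4 = 15.2 points with four, although the risk per cycle is the same.

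**Step 3: vary the assumptions.**
- q = 15%: hold probability in Arm A is 0.18, 0.41 or 0.64 for two, three or four cycles (cycle 1 only, 0.04); in Arm B 0.18, 0.24 or 0.31 (0.11).
- q = 10%: rates are 15.2% to 24.1% in Arm A against 11.7% to 14.6% in Arm B.
- Section 13.1's text assigns 14% and 29% to the opposite blast groups. Then r in Arm B is 0.33 × 0.14 + 0.67 × 0.29 = 0.24, and its rate at q = 20% is 23.8% to 29.4%.
- All of r start cycle 2, half continue at each later step, and later-cycle risk is halved: 27.7% against 22.5%, with hold probability about 0.36 in each arm.
- Looks taken before later cycles finish (about two Arm A patients a month, from the 2:1 share of three a month in Section 13.2): simulated hold probability in Arm A at q = 20% is about 0.38 with two cycles to about 0.82 with four. If in addition only half of those eligible start each further cycle, at half the risk, it is about 0.19 against 0.12 in Arm A, and about 0.30 against 0.26 in Arm B.

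**The case against.** The strongest reply is that an event in cycle 3 is real toxicity of the regimen as given, and a safety rule may properly count it. That stands. The documents do not show whether the 30% and 20% limits were meant per cycle or for the whole course. If for the whole course, 20% per cycle is too high an input.

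The Section 13.4 tables are also sound. They are indexed by the true rate per patient, and they hold for whatever rate the chosen window produces. What is missing is the definition of the event.

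A reader might infer that the plan counts events over four cycles. It does not say so; it is silent, and a cycle 1 reading is also open.

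A reader might infer that the rule is biased against the more active arm. Each arm is judged against its own limit, the rule never compares them, and Arm B's hold probability rises too. With two cycles at 15% per cycle, both arms are at 0.18.

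A reader might expect PR and MR patients to widen the gap. Without PR and MR rates by arm the direction is unknown; more PR and MR in Arm B would narrow it.

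Finally, the consequences are limited. A crossing holds enrollment and prompts a consultation, the primary CR/CRi analysis is untouched, and Section 13.5 specifies no between-arm test of toxicity.

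**Conclusion.** The point holds as a gap in definition that affects comparability. Sections 13.4, 13.5 and 13.7.1 set no end to counting, and cycles after the first depend on response. The rates serving the first secondary objective can therefore compare arms over unequal treatment. With equal risk of 20% per cycle and the design CR/CRi rates as the share continuing, the gap is about 6 to 15 points. The upper end requires four cycles for every responder, which is a ceiling because further cycles are optional. The figures also assume independent cycles and risk unrelated to response. Under all-cycle counting the hold probability rises in both arms, by an amount that depends heavily on how many patients continue and how much is complete at each look.

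Severity is minor to moderate: the toxicity comparison needs a defined window, but nothing here invalidates the stopping tables or the primary analysis.

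**What to change.** **Section 13.5.** Report and compare by arm the rate of each listed event, and of any listed event, with onset in cycle 1. Neutropenia that begins in cycle 1 should be followed past day 60 before it is classified, because the recovery assessment in Section 10 falls at day 28 to 42, too early for the 60-day event. Show separately the all-cycle rate per patient, and later-cycle events per cycle started, with the number of patients starting each cycle.

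**Section 13.4.** The sponsor should state which cycles the 30% and 20% limits refer to and, at any hold, give CTEP the counts by cycle. Later-cycle events should not be removed from the safety rule to solve a comparability problem: that would take treatment-related deaths in cycles 2 to 4 out of the formal hold.

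**Cost.** One extra table and slightly more analysis. No new data are needed, because Section 7 already has adverse events entered by course or cycle. The cycle 1 rate does not describe the cumulative burden of treatment, which is why the all-cycle table stays beside it.
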